214 in effect. More details are provided below for each pre-specified comparison.

215 10.2.1 Effect of aerobic-resistance exercise

216 To address objective 1 (the effect of supervised aerobic-resistance exercise on
217 cognitive function), the intervention arms providing exercise intervention (arm 1 to 4) will
218 be collapsed as one category and compared to the control (arm 5). The new
219 independent variable will be created to represent exercise intervention: aerobic-
220 resistance exercise intervention (collapsed arm 1 to 4), and control exercise intervention
221 – BAT – (arm 5). The new intervention variable will be fitted into the same linear mixed
222 model described above. Using the interaction between exercise intervention x time, the

223 change in primary outcome will be contrasted between participants receiving the
224 aerobic-resistance exercise and those not receiving the aerobic-resistance exercise.

225 10.2.2 Effect of adding cognitive training

226 The objective 2 (the effect of adding cognitive training to aerobic-resistance exercise on
227 cognitive function) will be examined by pooling the intervention arms providing both
228 exercise and cognitive intervention (arm 1 and 2) and pooling the intervention arms
229 providing exercise intervention but not cognitive intervention (arm 3 and 4). A new
230 independent variable will be created for addition of cognitive training: both exercise and
231 cognitive intervention (pooled arm 1 and 2) and exercise but no cognitive intervention
232 (pooled arm 3 and 4). Using the interaction term in the linear mixed model, the contrast
233 will be made between the two collapsed arms to assess whether the effect of adding
234 cognitive training to aerobic-resistance exercise differ from aerobic-resistance exercise.
235 If there is a significant difference observed, the two collapsed arms will be compared to
236 the control arm (arm 5). This marginal analysis will allow to evaluate the main effect of
237 aerobic-resistance exercise alone (pooled arm 1 and 2) and aerobic-resistance exercise
238 with cognitive training (pooled arm 3 and 4) compared to the control (arm 5) with higher
239 power (as a result of increase in sample size).^{5,8}

240 10.2.3 Effect of adding vitamin D supplements

241 The objective 2 (the effect of adding vitamin D to aerobic-resistance exercise on
242 cognitive function) will be examined by pooling the intervention arms providing both
243 exercise and vitamin D intervention (arm 1 and 3) and pooling the intervention arms
244 providing exercise intervention but not vitamin D (arm 2 and 4). A new independent
245 variable will be created to represent addition of vitamin D: both aerobic-resistance
246 exercise and vitamin D intervention (pooled arm 1 and 3) and aerobic-resistance
247 exercise but no vitamin D intervention (pooled arm 2 and 4). The linear mixed model will
248 be repeated using this new independent variable and the two pooled arms will be
249 compared. This will allow to explore whether adding vitamin D to aerobic-resistance
250 exercise improve the outcome compared to the aerobic-resistance exercise. If a
251 significant difference is observed, the two pooled arms will be compared to the control
252 arm (arm 5) to assess the main effect.

253 10.2.4 Effect of multidomain intervention

254 The objective 4 (effect of multi-domain intervention (aerobic-resistance exercise +
255 cognitive training + Vitamin D supplement) on cognitive function) will be assessed using
256 the time x intervention arm interaction fitted in the linear mixed model in section 10.2.
257 The interaction term between time x intervention arm 1 will represents the effect of
258 multidomain intervention (arm 1) compared to the control (arm 5).

259 **10.2.5 Long-term effect: From Baseline and Post-intervention to Follow up**

260 The long-term intervention effect from baseline and post-intervention to follow-up
261 (Month 12) will be assessed using the linear mixed model. Time will be used as a
262 categorical variable (Baseline, Month 6, and Month 12). Individuals with incomplete
263 follow up assessments will still be included in the linear mixed model.

264 **10.2.6 Post-hoc analyses**

265 ADAS-Cog-Plus is a construction proposed originally by Skinner et al.⁹, adding extra
266 tests for executive function and verbal fluency to increase sensitivity to detect
267 progression from MCI to dementia. Post hoc analyses will be performed to explore the
268 effect of intervention on ADAS-Cog-Plus scores by adding individual Plus items, one by
269 one, to ADAS-Cog-13.

270 **10.3 Secondary Outcomes Analyses**

271 The secondary analysis will be performed in an intention-to-treat population and a per-
272 protocol population. The details of the statistical analysis plan for secondary outcomes
273 are not included in this analysis plan as the secondary outcome analyses will not be
274 included in this primary manuscript and performed afterwards.

275

276 **11. Data management and Quality Control**

277 All sites will use the same data collection forms to maintain consistency. Data storage
278 and monitoring procedures will be performed using the LORIS (Longitudinal Online
279 Research and Imaging System) system platform for uploading data specially developed
280 for the SYNERGIC study by CCNA informatics team platform. Data quality will be
281 assessed either using Excel and the online CCNA-LORIS platform database. All data
282 will be entered and managed in LORIS database, and a double data entry system will
283 be used to assure accuracy of entry. Outliers and missing data will be managed using
284 statistical software adopted for the final analysis. Original completed CRFs will be
285 uploaded to the media module, initial and double data entries will be performed, and
286 arising conflicts will be resolved in the conflict resolver module. Once the conflicts are
287 resolved, the data will be validated by the clinical team and will be ready for release
288 through the data query tool.

289 See: <https://www.frontiersin.org/articles/10.3389/fninf.2018.00085/full>

290

291

292 12. Programming Plans

293 Data analysis will be performed using statistical software SPSS (SPSS version 23.0,
294 SPSS Inc., Chicago, IL) and R version 3.5.1 (R Project for Statistical Computing).

295

296

297 1. Cohen J. *Statistical power analysis for the behavioral sciences*. 2nd ed. Hillsdale, N.J.: L.
298 Erlbaum Associates; 1988.

299 2. Montero-[name] M, Almeida QJ, Burhan AM, et al. SYNERGIC TRIAL (SYNchronizing
300 Exercises, Remedies in Gait and Cognition) a multi-Centre randomized controlled double
301 blind trial to improve gait and cognition in mild cognitive impairment. *BMC Geriatr.*
302 2018;18(1):93.

303 3. Skinner J, Carvalho JO, Potter GG, et al. The Alzheimer's Disease Assessment Scale-
304 Cognitive-Plus (ADAS-Cog-Plus): an expansion of the ADAS-Cog to improve
305 responsiveness in MCI. *Brain Imaging Behav.* 2012;6(4):489-501.

306 4. Crane PK, Carle A, Gibbons LE, et al. Development and assessment of a composite score
307 for memory in the Alzheimer's Disease Neuroimaging Initiative (ADNI). *Brain Imaging Behav.*
308 2012;6(4):502-516.

309 5. McAlister FA, Straus SE, Sackett DL, Altman DG. Analysis and reporting of factorial trials: a
310 systematic review. *JAMA.* 2003;289(19):2545-2553.

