5. STUDY POPULATION

5.1 PARTICIPANTS, RECRUITMENT, STRATIFICATION, AND BLINDING

We will target older adults aged 60 and over with MCI. Interventions will be done across five sites: London (lead and sponsor site, target recruitment: 70 participants), Waterloo-University of Waterloo (target recruitment: 25), Waterloo-Wilfrid Laurier University (target recruitment: 20), Montreal (target recruitment: 30) and Vancouver (target recruitment: 55). Each intervention site may have more than one recruitment center. For those who are interested in participating, a consent and screening session will be arranged as described in our participant flowchart, Figure 3.

Once informed consent is obtained, we will perform the screening tests. Those who remain eligible after the screening session including the Physical Activity Readiness Questionnaire Plus (PARQ+) and who provide written recommendation from their physician or site physician indicating their appropriateness to participate in an aerobic-based exercise training program will proceed to baseline assessments. Participants will be informed that they will be randomly assigned to one of five arms by the research coordinator and will be blinded to the investigators' hypothesis as to which is the preferred intervention arm.

All groups will have an equal volume and frequency of contact with trainers over the 12 months of the study. All primary and secondary outcomes will be obtained and analyzed by blinded assessors on different days to the training programs.

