7.0 STUDY PROCEDURES

Baseline measurements will be obtained prior to randomization. There will be three measurement sessions: baseline, 6 months, and 12 months (Figure 1, Appendix I). Outcomes will be assessed by

trained assessors blinded to group allocation. As outlined in point 5, there are five main interventional/assessment centers. Recruitment will be occurring primary in clinics serving MCI populations already identified in each site and from the community. In addition, older persons belonging to the community will be invited to participate through different recruitment methods, including case findings by phone interviews and recruitments in primary care and geriatrics clinics. Strategies to increase the awareness of the study will be implemented through explanatory brochures and a dedicated webpage: “www.synergictrial.com”. Results of the mobility tests and laboratory examinations can be provided to the participant and to her/his family physician upon their request. Transportation will be paid when necessary. Finally, dissemination of our findings will be conducted in the community through open discussion sessions and booklets and publications in the local newsletter.

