7.2 BASELINE EVALUATION (VISIT 2)

Participants will undergo rigorous baseline evaluations, which will take place up to four weeks after the screening session. Baseline assessments will include neuroimaging, neuropsychological, and gait measures. These will be repeated at the 6-month and 12-month follow-up.

1. Log return of the Physical Activity Device
2. Blood Draw
3. Clinical Medical Questionnaire
4. Quality of Life Questionnaire (SF-36)
5. ADAS-Cog Plus Tests (ADAS-Cog 13 Tests, plus the Digit Span Forward and Backward WAIS-III, TMT A and B, Digit Symbol Test, Boston Naming Test)
6. D-KEFS Colour Word Interference Test
7. Short Physical Performance Battery (SPPB)
8. Six Minute Walk Test (6MWT)
9. Dual task control assessment while seated (mental task)
10. Gait assessment using Gait Mat and Accelerometers (when available)
11. Schedule Neuroimaging

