7.2.1 TREATMENT ALLOCATION

Randomization Once informed consent has been obtained and the baseline assessment has been completed, participants will be allocated to each of the 5 arms. The randomization sequence of the participants will be generated in each site with a minimum of 4 participants recruited using a central, web-based randomization service. The Research Pharmacy will assign the ‘vitamin D/placebo kits’ in compliance with randomization lists generated by a computer program and allocation to groups will be done with sequentially numbered opaque sealed envelopes. A block randomization by 5 will be applied to ensure an appropriate balance of the characteristics of participants between each arm. Permuted

blocks of varying size will be employed to ensure balance over time. After baseline assessment, research personnel not involved in measurement or intervention will access the web-based randomization service to determine the group allocation.

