7.2.2 BLINDING

In order to minimize a source of bias, this trial is planned to be a double-blinded study. Research personnel performing the outcome assessments will be blinded to group allocation. Participants will be blinded of intervention.

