The 6MWT is used to quantitatively measure participants' exercise capacity by measuring the maximum distance that a person can walk in 6 minutes. The test is a modification of the 12-min walk/run test originally developed by Cooper [54] and is commonly used as an assessment of exercise capacity. The 6MWT is useful for predicting the maximal oxygen uptake related to cardiorespiratory fitness and is easily administered in clinical settings [55]. The 6MWT is believed to be a useful instrument because of its ease of administration and similarity to normal daily activities. It is a submaximal test of aerobic capacity which has been successfully used in MCI populations [56].

The 6MWT will be assessed by licensed and trained physical therapists. The participants are instructed to walk from one end of a 10-meter course to the other and back again as many times as possible in 6 min, while under the supervision of a physical therapist. After each minute, participants were informed of the time elapsed and were given standardized encouragement. The distance (meters) walked in 6 min was recorded [55].

Short Physical Performance Battery (SPPB)

It is a widely used instrument for quantifying lower extremity function and mobility in older adults. It is a group of measures that combines the results of the gait speed, chair stand and balance tests [57]. It has been used as a predictive tool for possible disability and can aid in the monitoring of function in older people. The scores range from 0 (worst performance) to 12 (best performance). The SPPB has been shown to have predictive validity showing a gradient of risk for mortality, nursing home admission, and disability. [58]

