APPENDIX I

Procedure	Visit 1 Screening	Visit 2 Baseline	Randomization	Visit Table		
				Visit 3 6M Visit	Telephone Follow-up (9M post-Baseline)	Visit 4 12M Visit
Written Informed Consent	X					
Demographic Information	X					
PASE Questionnaire	X			X		X
Mini Mental State Examination (MMSE)	X					
Montreal Cognitive Assessment (MoCA) Logical Memory 1 & 2 *	X			X		X
CERAD Word List Recall *						
Geriatric Depression Scale (GDS-30)	X			X		X
Generalized Anxiety Disorder 7 (GAD-7)	X			X		X
Clinical Dementia Rating (CDR)	X			X		X
Physical Activity Readiness Questionnaire Plus (PAR-Q +)	X					
ADCS-ADL and IADL	X			X		X
Clinical Medical Questionnaire		X		X		X
Dual Task Control Assessment		X		X		X
Six Minute Walk Test (6MWT) ^		X		X		X
Quality of Life Questionnaire (SF-36)		X		X		X
ADAS-Cog 13 (+ tests **)		X		X		X
Digit Span Forward and Backward WAIS-III **		X		X		X
TMT A and B **		X		X		X
Digit Symbol Test **		X		X		X
Boston Naming Test **		X		X		X
Colour Word Interference Test		X		X		X
Envelope Test		X		X		X
Short Physical Performance Battery (SPPB)		X		X		X
Gait Assessment using Gait Mat and accelerometers (when available)		X		X		X
Neuroimaging (MRI)		X		X		
Blood Draw		X		X		X
Falls Calendar ^^		X		X	X	X

* These tests are implemented to harmonize with inclusion criteria for COMPASS-ND and are not mandatory if the MoCA score ≤ 24 .

** Testing included in the ADAS Cog Plus.

^ 6MWT can be completed at the Baseline Visit or at Day 1 of intervention sessions at the gymfacilities. Please note date and location of the 6MWT in patient file.

^^ Calendar will be given to participant to complete and will be submitted to Research Staff at exercise training.

1
2
3
4
5
6
7

Statistical Analysis Plan (SAP)

10
11
12
13 **SYNchronizing Exercises, Remedies in Galt and Cognition (SYNERGIC) Trial**

13 SYNchronizing Exercises, Remedies in Galt and Cognition (SYNERGIC) Trial

14
15
16
17
18
19
20
21
22
23

Version: Final

Authors: [name], PhD, University of Western Ontario
[name](c), University of Western Ontario
[name], Parkwood Institute
[name], University of Western Ontario and Robarts Research Institute
[name], University of Western Ontario

Date: Sept 2022

24
25
26
27
28
29
30

31 1. Introduction

32 The SYNERGIC TRIAL (SYNchronizing Exercises, Remedies in Galt and Cognition) is
33 a randomized, phase II, fractional factorial, five-arm, double-blind controlled study
34 evaluating the effect of aerobic-resistance exercise with and without cognitive training

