Six Minute Walk Test (6MWT) ^b		X	X		X
Neuroimaging (MRI)					
Blood Draw		X	X		
Falls Calendar ^c		X	X	X	X

94 ^aTesting included in the ADAS-Cog plus95 ^bThis test may be completed at the gym facility on the first day of intervention96 ^cCalendar will be given to participant to complete and will be submitted to Research Staff at exercise training97

7. Determination of Sample Size

98 Sample size calculation is based on changes in our primary outcome: global cognitive
 99 function measured using the Alzheimer Disease Assessment Scale Cognitive 13 and

100 the plus variant (ADAS-Cog 13 and plus). A target sample of 200 participants (40 per
 101 arm) was determined based on 80% power to detect either main effects or an
 102 interaction of at least a moderate (Cohen's $d \sim 0.5$)¹ effect size of changes in the ADAS-
 103 Cog-13.² The final sample size accounted for a 15% attrition.

104

105 **8. Primary Outcomes**

106 Primary outcome will be changes in cognitive function measured with the ADAS-Cog 13
 107 items (ADAS-Cog-13) and the plus variant (ADAS-Cog-plus) at endpoint, 6 Month.
 108 Improvement at endpoint in either variant is considered evidence of efficacy.

109 **8.1 Change in cognitive function on ADAS-Cog-13 at post-intervention (Month 6)**

110 The ADAS-Cog 13 consists of 13 brief cognitive tests assessing memory, language,
 111 attention, concentration and praxis. The individual tests are listed in Table 2. Scores
 112 range from 0 to 84, with higher scores indicating severe cognitive impairment.

113 **8.2 Change in cognitive function on ADAS-Cog-Plus at post-intervention (Month 6)**

114 Four additional tests focusing on executive function will be added to the ADAS-Cog 13
 115 to comprise the plus variant³ (Table 2). Scores will be transformed into an algorithm
 116 validated by Crane et al.⁴ The higher scores will indicate severe of cognitive impairment.

117
 118 Table 2. Individual tests included in the ADAS-Cog

ADAS-Cog-13	ADAS-Cog-Plus
Word recall	Word recall
Delayed word recall	Delayed word recall
Following commands	Following commands
Constructional praxis	Constructional praxis
Ideational praxis	Ideational praxis
Naming objects	Naming objects
Orientations	Orientations
Word recognition	Word recognition
Remembering instructions	Remembering instructions
Comprehension	Comprehension
Word finding	Word finding
Spoken language	Spoken language
Number cancellation	Number cancellation
	Trial Making A and B
	Digit symbol substitution

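### The Day 1 option for the baseline six-minute walk permits a post-randomisation, training-day baseline, against the protocol's own rules, for the only scheduled test described as measuring aerobic capacity

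*Combined protocol and SAP*

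**What the plan says.** Protocol section 7.2 lists the six-minute walk test (6MWT) among the Visit 2 baseline assessments. Two footnotes then widen its timing. The one under the Appendix I visit table says "6MWT can be completed at the Baseline Visit or at Day 1 of intervention sessions", at the gym, and asks staff to note the date and location in the patient file. Note b to SAP Table 1 says the "test may be completed at the gym facility on the first day of" intervention.

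Three rules in the body of the protocol bear on this:

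- Section 7.0: "Baseline measurements will be obtained prior to randomization".
- Section 7.2.1: "Once informed consent has been obtained and the baseline assessment has been completed, participants will be allocated to each of the 5 arms".
- Section 5.1: "All primary and secondary outcomes will be obtained and analyzed by blinded assessors on different days to the training programs".

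None of the three states an exception for the 6MWT. Section 7.2.2 adds that "Research personnel performing the outcome assessments will be blinded to group allocation".

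The 6MWT is a named mobility outcome in SAP section 9.3. Protocol section 7.6.6 says of it: "It is a submaximal test of aerobic capacity which has been successfully used in MCI populations".

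**The concern.** A baseline taken after allocation no longer has the protection of randomisation. Before allocation, any difference between arms in baseline walking distance is chance. After allocation, and on a day when the arms do different things, it can also reflect the arm itself. Such a difference then enters the change from baseline, which is the quantity of interest.

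The outcome at stake supports a stated hypothesis. Secondary hypothesis 3 (protocol section 2.1.b) predicts that exercise raises fitness, including aerobic capacity, relative to the control condition. The 6MWT is the only scheduled assessment that the protocol describes as a test of aerobic capacity. If its baseline can be shifted by allocation, the evidence for that part of the hypothesis is weakened, and the plan has no rule for handling the affected values.

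**Working it through.** No published figure is involved, so the check is of sequence, followed by the algebra of the possible bias.

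**Order of events.**

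1. Consent and screening at Visit 1 (protocol 7.1).
2. Baseline assessment at Visit 2, including the 6MWT (7.2).
3. Allocation, once baseline is complete (7.2.1).
4. Day 1 of training, with content set by arm (6.1).

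A walk on Day 1 falls at step 4. Set against the rules:

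| Rule | Requires | Day 1 walk |
|---|---|---|
| 7.0 and 7.2.1 | Baseline before allocation | After allocation: conflict |
| 5.1, timing | Outcomes on non-training days | On a training day: conflict |
| 5.1 and 7.2.2, assessor | Blinded assessor | Not changed by the footnotes: no conflict shown |

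The notes to protocol Figure 2 place baseline within one week of starting the intervention. That limits the gap between the two; it does not permit testing after allocation.

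**How the arm could reach the baseline.** In arms 1 to 4 a session has circuit strength work, with resistance set so that the last repetition of each set is exhausting (6.1.2). In weeks 1 to 4 this is followed by two 10-minute aerobic sets at Borg 5-6. In arm 5 it has a 5-minute machine warm-up, 50 minutes of stretching, mostly seated, and 5 minutes of relaxation (6.2.3); the SAP calls this control balance and toning. A walk done after the session would follow quite different exertion by arm. Neither footnote says whether the walk comes first.

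**Size and direction.** Let p be the share of participants with a Day 1 baseline, taken as the same in every arm. Let d be the mean shift in that baseline, in metres, in the exercise arms minus the shift in the control arm.

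- Bias in the exercise-control difference in change from baseline = -p × d.
- In a model adjusted for baseline with slope b, bias = -b × p × d.

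If walks follow the session and exertion shortens them more in arms 1 to 4, d is negative and the bias is positive, towards a larger apparent gain with exercise. If p = 0 or d = 0, the bias is zero. The case d = 0 includes Day 1 effects that are present but equal across arms.

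The documents give neither p nor d, nor a standard deviation for the 6MWT against which a shift could be judged. No numerical result follows.

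**Which formula applies.** Protocol section 8 names one-way analysis of variance on six-month change for gait performance and secondary cognitive outcomes; it does not name the 6MWT. SAP section 10.3 leaves the secondary analyses to a later plan. Whether the bias would enter in full or scaled by b is therefore open.

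**The case against.** The strongest reply is that this is a practical and traceable allowance on one secondary outcome. The date and place of the walk must be recorded, so affected values can be found. SAP section 9 keeps secondary outcomes out of the primary manuscript, and ADAS-Cog has no such exception. All of that stands and limits the weight of the point. It does not remove the conflict: recording a date identifies a post-randomisation baseline, but no section says what to do with it.

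Two stronger readings are tempting, and the documents do not support them.

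- **That assessor blinding is broken.** The footnotes change the day and place, not who tests. Section 7.2.2 still applies, and section 7.6.6 still assigns the 6MWT to trained physical therapists. That a tester at the gym would see the participant's arm is an inference; nothing says that the arms train together or that the tester watches the session. Blinding may be harder to keep there, but a breach is not shown.
- **That the baseline is biased in favour of exercise.** This needs the walk to follow the session, and the order is not given. If the walk comes first, there is no fatigue from the session, and any effect would have to come through the participant's or the tester's awareness of the arm. The protocol says participants are blinded to the intervention.

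**Conclusion.** The contradiction is certain: two current footnotes permit what sections 7.0, 7.2.1 and 5.1 rule out. The consequence is a possibility, not a demonstrated bias. Allocation could affect the baseline 6MWT, and so distort the exercise-control contrast for the aerobic capacity part of secondary hypothesis 3.

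The direction towards exercise is plausible only if walks follow the session. The size depends on the share of Day 1 walks and on the difference between arms in the Day 1 effect, both unknown. A figure in metres would rest on unsourced assumptions. The primary analysis is untouched. The point deserves correction because the rules conflict and the remedy is cheap, not because harm to the trial's main conclusion is likely.

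**What to change.** Reconcile the footnotes in Appendix I and SAP Table 1 with protocol sections 5.1, 7.0 and 7.2.1 by removing the Day 1 option. The baseline 6MWT is then done before randomisation, on a non-training day, by the blinded assessor.

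For walks already done on Day 1, flag them from the recorded date and location. Add to the secondary analysis plan, which the SAP leaves for later, a 6MWT sensitivity analysis that excludes those baselines, and report how many there are in each arm. If baseline collection has finished, as a SAP marked final in September 2022 suggests, this analytic step is the part that still helps.

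Setting the Day 1 baselines to missing in the main 6MWT analysis is not an equal alternative. In an analysis of change scores a missing baseline drops the participant, and the number lost could be large.

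The cost is two footnotes and a short addition to the analysis plan, with no new test. Some walks must be booked earlier, and the sensitivity analysis has fewer participants and so less precision.
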